a positive result followed by a colonoscopy within 90 days. Due to the COVID-19 pandemic preventive screening was postponed for a time, which created a backlog of patients who need screening, including screening for CRC. To adjust for this delay, additional medical record review will be conducted to assess for any incident CRC screening episode within 18-months after randomization and intervention. A **secondary outcome measure** will include the rate of positive MT-sDNA test follow up to diagnostic colonoscopy. We anticipate that positive MT-sDNA tests will have higher follow-up rates to colonoscopy within 90 days than other studies have reported of positive FIT/gFOBT (55.6% followed up with colonoscopy)⁵⁴ due to the patient navigation system included in the MT-sDNA test model. We will also compare incident CRC and advanced adenoma [adenomatous polyp ≥ 1 cm or containing $>25\%$ villous component or high-grade dysplasia, or sessile serrated adenoma/polyp ≥ 1 cm] detection between the three arms. We will also incorporate into our secondary analyses measures from the process evaluation (e.g., patient satisfaction with MT-sDNA vs colonoscopy, provider attitudes and beliefs) as well as other moderating factors to determine their roles in explaining the magnitude and direction of the results we find.

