questions about how the patient felt about using that specific test, and why they chose that test over the other one. It is important they also know the test result so they can anticipate any questions the patient might have, especially if there was an abnormal finding. We will also conduct a semi-structured open-ended telephone survey with intervention participants who requested the MT-sDNA test for CRC screening, were sent a test kit but did not complete and return it to the laboratory for analysis within the 12-month post intervention period. The purpose of the survey is to learn about the underlying barriers and reasons patients did not complete this screening method. Similarly, we will survey patients who chose to complete screening with a colonoscopy, scheduled an appointment, but never completed a procedure to assess barriers to patients completing the procedure even after it was scheduled. A study staff member at ANTHC will contact patients and conduct the surveys. We will verify patients' address and phone number at the time of the surveys to assess whether we sent the kit to the correct address, which could relate to non-adherence of screening with the MT-sDNA test as well as update YKHC medical records with patients' current contact information. We will use IRB- and tribally-approved study flyers and information sheets located at the Alaska Native Medical Center in Anchorage, AK and participating rural THOs to further recruit participants per IRB and tribal review.

2.5 STATISTICAL ANALYSIS.

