3 HUMAN SUBJECTS PROTECTION

3.1 RECRUITMENT AND INFORMED CONSENT

Quantitative Study: After obtaining Alaska Area Institutional Review Board (IRB) and appropriate Tribal review and clearance, a list of eligible patients will be drawn from each participating THOs electronic medical record (EMR) system. Each healthcare system in the ATHS uses comprehensive EMRs and administrative databases that will be used to collect contact information (e.g., phone number(s) and mailing address), demographic information (e.g., age, sex, and race and ethnicity), identify patients due for screening, provider orders, screening test completion, and pathology results. Prior history of CRC screening, including time since the last screening, will be retrospectively collected from EMRs. Current Procedural Terminology, Healthcare Common Procedure Coding System, and laboratory codes will be used to ascertain receipt of screening and screening method, regardless of indication. See Appendix A for list of variables to be collected. All variable data collected for this study will be stored in REDCap (Research Electronic Data Capture), a secure HIPAA compliant database system.

Communities will be randomized to one of two interventions: high intensity or medium intensity. The high intensity intervention will include navigated outreach, a mailed MT-sDNA kit, mailed culturally appropriate educational material describing CRC screening options available, and follow-up reminders (Study Group 1). The medium intensity intervention will include mailed culturally appropriate educational material describing CRC screening options available, including MT-sDNA, and navigated follow-up outreach reminders (Study Group 2). Participants will be recruited by mail and phone calls, depending on the intervention arm. All remaining communities in the region served by that THO will receive usual care and will not have direct outreach.

Patients who requested MT-sDNA for CRC screening, received a kit, but did not return it will be contacted to assess reasons for non-adherence. Survey data will be collected verbally by phone by an ANTHC study team member and stored in REDCap, a secure HIPAA compliant database system. This data will be stored with identifying information such as name and phone number, which is needed to contact patients for the phone survey but no personally identifying information will be included in the reporting of the non-adherence data analysis.

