Waiver of Consent: As individuals will be selected for each trial arm based on their randomized community, we requested a waiver of informed consent for eligibility and group assignment from the Alaska Area IRB as well as the Alaska Native Tribal Health Consortium (ANTHC) and the ANTHC and SCF Privacy Officers, who have given approval for the waiver of consent. We will also request a waiver of informed consent from participating THOs prior to study implementation.

The rationale for the waiver of consent is that the study will randomize by community (cluster randomization) so that everyone who is eligible for CRC screening in that community will be offered the same intervention (or usual care). The disclosure of the study purpose as part of the consent process to individuals would bias the research so that the results will not be meaningful, since the study is trying to determine on a community level how much offering these different types of CRC screening interventions would help increase overall community screening rates. The purpose of the waiver of informed consent is to avoid potential selection/volunteer bias. Additionally, if participants are consented, they will know which intervention community they are in, and so there might be bias resulting from that as well. Patients who did not return their mt-sDNA kit for CRC screening and those that scheduled a colonoscopy but never completed it will be contacted for a phone survey and fall under this waiver of consent. These are patients who participated in the intervention and are being followed up with to assess why they chose to screen with mt-sDNA or colonoscopy, but ultimately did not return their kit or complete a procedure to complete screening.

To help address potential concerns raised by this type of study design, the regional THOs and their Privacy Officers will be asked to approve the waiver of consent prior to study implementation. Clinic staff (front desk, Community Health Aides, midlevel providers) in intervention communities will be

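### Phone surveys of non-completers, made in the outreach arms only, may fall inside the 18-month outcome window and prompt screening there

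*Combined protocol and SAP*

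**What the plan says.** Section 2.4 (qualitative study) describes a "semi-structured open-ended telephone survey with intervention participants who requested the MT-sDNA test for CRC screening" who "were sent a test kit but did not complete and return it to the laboratory for analysis within the 12-month post intervention period". It continues: "we will survey patients who chose to complete screening with a colonoscopy, scheduled an appointment, but never completed a procedure". No period is attached to this second survey. Of the calls themselves it says: "We will verify patients' address and phone number at the time of the surveys to assess whether we sent the kit to the correct address". Contact details in the medical record are updated at the same time.

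Section 3.1 repeats the kit survey without the 12-month condition: "Patients who requested MT-sDNA for CRC screening, received a kit, but did not return it will be contacted to assess reasons for non-adherence". The waiver-of-consent text there covers both groups of non-completers and places both in the intervention arms: "These are patients who participated in the intervention and are being followed up with to assess why they chose to screen". Usual care is different: "All remaining communities in the region served by that THO will receive usual care and will not have direct outreach".

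Section 2.3 defines the primary outcome over 1 year. To allow for the COVID-19 backlog, it adds a second record review for "any incident CRC screening episode within 18-months after randomization and intervention".

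**The concern.** A call from study staff about an uncompleted test, with a check of where the kit was sent, resembles a reminder. It is not among the components of either intervention listed in sections 2.3 and 3.1. It goes only to people in the outreach arms who have not completed the test or procedure they chose, and usual care has no counterpart. If it is made while screening still counts, the 18-month contrast measures outreach plus survey contact.

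The 18-month review is the plan's stated adjustment for the pandemic delay, so readers will give it weight. A programme that later delivered only the described outreach would not reproduce any part of the effect that came from the survey calls.

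**Working it through.** **Timing and exposure, from the text**

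| Item | Who | Earliest | Latest |
|---|---|---|---|
| Kit survey (2.4) | Intervention participants who requested and were sent a kit | Month 12, by its entry condition | Not stated |
| Colonoscopy survey (2.4, 3.1) | Intervention participants who scheduled but did not complete | Not stated | Not stated |
| Usual care (3.1) | No direct outreach | n/a | n/a |
| Primary outcome (2.3) | All arms | Month 0 | Month 12 |
| Additional outcome (2.3) | All arms | Month 0 | Month 18 |

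If the 12-month survey condition and the 1-year outcome run from the same start, the kit survey can overlap the outcome only in months 12 to 18. The colonoscopy survey could overlap any part of either window. No section holds the calls until month 18, brings call dates into the analysis, or says how screening after a call is handled.

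**The plan's own figures.** Section 2.5 gives 59% without intervention, 10-point differences, 775 per arm and more than 80% power at alpha 0.05. Section 1.1 expects gains of 10% (medium) and 20% (high). Read as percentage points, the rates are 59%, 69% and 79%. A two-sided comparison of proportions without clustering gives 98.4% power for 59% v 69% and about 99.5% for 69% v 79%, so the stated power is reproduced. This point does not dispute it.

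**Size of a possible effect.** The documents give no number surveyed, no contact rate and no rate of screening after a call, so these are assumptions.

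Shift in the arm's 18-month rate = unscreened share × share of those who qualify for a call × share reached × share of those reached who then screen because of the call.

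Unscreened shares at the plan's rates are 1 − 0.79 = 0.21 (high), 1 − 0.69 = 0.31 (medium) and 1 − 0.59 = 0.41 (outreach has no true effect). Assume that everyone unscreened qualifies (an upper limit), 60% are reached and 10% of those are prompted:

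- High: 0.21 × 1 × 0.60 × 0.10 = 0.0126, about 1.3 points
- Medium: 0.31 × 1 × 0.60 × 0.10 = 0.0186, about 1.9 points
- No true effect: 0.41 × 1 × 0.60 × 0.10 = 0.0246, about 2.5 points

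**Range.** Let 25% to 100% qualify, 30% to 70% be reached and 5% to 20% be prompted:

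- High: 0.21 × 0.25 × 0.30 × 0.05 = 0.08 points, to 0.21 × 1 × 0.70 × 0.20 = 2.9 points
- Medium: 0.12 to 4.3 points, by the same products with 0.31
- No true effect: 0.15 to 5.7 points, with 0.41

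In the last case, with 775 per arm and no clustering, the chance of a false finding in favour of outreach rises from 2.5% to between 2.9% and 64%. The upper figure needs every assumption at its extreme.

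**The case against.** The strongest reply is that the plan sets only an earliest time for the kit survey. Nothing says that calls are made in months 12 to 18, and calls made later do no harm. The stated purpose is to learn about barriers, and no section says that the caller offers a new kit or books a procedure. The people called have already failed to complete despite the reminders in both interventions, and colonoscopy is not available all year at many regional hospitals (section 1). All of this stands. It makes a small effect plausible, but it does not keep the calls out of the window.

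Blinded record review (2.3) is no answer, because it protects how outcomes are ascertained and not how people behave. The intent-to-screen analysis (2.5) credits prompted screening to the assigned arm.

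Three stronger readings are tempting, and the documents do not support them:

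- **The kit survey biases the primary outcome.** Under section 2.4, non-return by 12 months is the condition for being called. Only the colonoscopy survey is undated. It is introduced as similar to the kit survey, so the same late timing may be intended.
- **High v medium is biased towards high because that arm is mailed kits.** Sections 2.4 and 3.1 limit the survey to people who requested MT-sDNA, and someone mailed an unrequested kit may not qualify. The direction is unknown.
- **Half or more of an outreach arm would be called.** At 50%, the same contact and prompting rates give 0.50 × 0.60 × 0.10 = 3.0 points. But 50% exceeds the 21% to 41% left unscreened at the plan's rates, and those surveyed are a subset of these. One caution applies: 59% is a current population rate, while section 2.4 excludes people already adherent. Uptake in the trial could be lower, and the unscreened share larger.

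**Conclusion.** The concern holds as a design risk to the 18-month comparison of outreach with usual care. As written, the plan allows an extra contact in the outreach arms only while screening still counts, and any bias in that comparison would favour outreach. The 1-year outcome is safe from the kit survey but not demonstrably safe from the colonoscopy survey.

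At the plan's rates the shift is at most about 1.3 to 2.5 points against a 10-point target. That rests on 60% reached, 10% prompted, every unscreened person qualifying and all calls falling before month 18. None of these comes from the documents, and the true figure could be negligible or larger. The point merits correction because the remedy is cheap, not because a large bias has been shown.

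**What to change.** State in section 2.4 that both non-completer surveys start only after each participant's 18-month outcome window has closed, and align section 3.1 with it. This removes the bias from these calls at both time points. It costs up to about six months' delay to the kit survey and somewhat poorer recall of reasons, with no extra patients or staff.

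If any calls are made earlier, record the date of each and report an additional 18-month analysis that counts screening after a call as not completed. Label it a conservative bound against outreach and not an unbiased estimate. It deletes events from the outreach arms only, including screening that would have happened without a call. Keep the 12-month outcome as primary.

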1.1. SPECIFIC AIMS

Aim 1. Identify patient-, provider-, and system-level factors associated with CRC screening preferences, uptake, and follow-up, using a theory-based, mixed methods multi-stakeholder formative and process evaluation. While our prior work shows that an intervention to improve screening is likely to be broadly feasible and accepted, we anticipate variation in adherence between communities. To identify reasons for that variation we propose to:

Sub-aim 1.a. Conduct a formative evaluation to assess community context and engage stakeholders in MT-sDNA intervention development including study design, protocol development, and implementation.

Sub-aim 1.b. Use the Health Belief Model^{28,29} to evaluate patient-level factors associated with test preference, screening adherence, and diagnostic follow-up.

Sub-aim 1.c. Conduct patient key informant and focus group interviews to identify factors that facilitate and impede screening uptake and effects among subgroups (sex, age, degree of rurality).

Sub-aim 1.d. Conduct a brief survey and key informant interviews among community health aides, providers, and tribal health system administrators using validated measures of intervention feasibility, acceptability, and appropriateness³⁰ to characterize provider- and system-level barriers and promotors to MT-sDNA implementation.

Aim 2. Test the hypothesis that multi-level high and medium intensity MT-sDNA community-based interventions, as compared with usual care, will increase CRC screening rates among AN people in rural/remote communities.

Sub-aim 2.a. Participants receiving high intensity intervention (navigated tribal health worker outreach, a mailed MT-sDNA kit, culturally appropriate educational material, and follow-up reminders) are expected to have a 20% increase in screening uptake while those receiving medium intensity intervention (mailed culturally appropriate educational material describing CRC screening options available, including MT-sDNA, and navigated follow-up outreach reminders) will have a 10% increase in screening uptake over those receiving usual care (screening recommendation at a clinic visit). A sample of 770 participants in at least six communities per study arm will be recruited.

Sub-aim 2.b. Measure the impact of sex, age, and rurality on the effect size of the intervention, MT-sDNA uptake compared to colonoscopy, and MT-sDNA follow up to diagnostic colonoscopy.

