Although this study will use a cluster-randomized design with the community as the unit of analysis, our research experience in rural Alaska communities indicates minimal within community influence on an individual's personal health decisions. Because an intra-class correlation near zero approaches a simple random sample design, for clarity in our power calculations we have approximated our design as a simple random sample.⁶⁰ The sample size allocation for this study is based on a pre-specified ability to detect an expected difference of 10% or more in screening participation rates for usual care vs any intervention as well as a difference of 10% or more in screening for high intensity vs medium intensity outreach. Given these expected improvements in screening rates, and the expected non-intervention screen rate of 59% based on current rates among AN people, we anticipate more than 80% power to detect a statistically significant difference between screening rates in our medium and high interventions, at alpha of 0.05. To achieve this, we will recruit a sample of 775 or more persons per study arm. An intent-to-screen principle will be used to analyze all eligible patients for the primary outcome: screening participation. All eligible communities will be randomly assigned to an intervention arm at baseline. Group assignment will not be shared because all patients will be randomized at the same time point. Outreach patients will be blinded to the presence of alternate interventions; usual care patients will be blinded to the presence of group assignment altogether.

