We will compare demographic characteristics (sex, age) between those screened using MT-sDNA and colonoscopy, as well as by intervention status (high intensity, medium intensity, usual care) in simple frequency tables. We will use multivariable models to assess the role of intervention status in determining screening rates, adjusting for potential confounders such as age, sex, and other demographic characteristics. Because our primary response is the proportion of persons screened (or the screening rate) we will utilize logistic and/or Poisson regression in our multivariable linear models. For Sub-aim 2.b we will examine how effectiveness of the interventions may vary by sex, age, and rurality using frequency tables and crossing outcome proportions by levels of sex, age, and rurality. Examination of interaction terms (sex by intervention, age by intervention, etc.) in multivariable models, as well as subset analysis as appropriate to illuminate such differences, will allow us to evaluate differences across these covariates in effectiveness of the intervention arms. For Sub-aim 2.c we will obtain an estimate of the sample quality under each of the three intervention conditions and also an estimate of the sample quality likely to result when these interventions are deployed to the larger population and compare those to national sample quality estimates (96%).

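### Section 2.5 allows Poisson regression for a common yes/no outcome with no robust variance or community term; with model-based Poisson errors, medium v high power would be about 74% on the plan's own assumptions

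*Combined protocol and SAP*

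**What the plan says.** Section 2.3 defines the primary outcome as whether a person completes an incident screening episode, so each person contributes a yes or a no. The only model statement for it is in section 2.5: "we will utilize logistic and/or Poisson regression in our multivariable linear models". The section adds adjustment for age, sex and other demographics. It does not say which model is primary or which effect measure will be reported. Neither section 2.5 nor any other section mentions a robust or sandwich variance, a dispersion parameter, generalised estimating equations or a random effect for community.

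The planning figures are also in section 2.5: an "expected non-intervention screen rate of 59% based on current rates among AN people"; an "expected difference of 10% or more in screening participation rates for usual care vs any intervention"; and "a difference of 10% or more in screening for high intensity vs medium intensity outreach". With 775 or more per arm, and treating the sample as a simple random sample, "we anticipate more than 80% power to detect a statistically significant difference between screening rates in our medium and high interventions", "at alpha of 0.05". Section 1.1 gives matching arm-level expectations: high-intensity participants "are expected to have a 20% increase in screening uptake", and medium-intensity participants "will have a 10% increase in screening uptake over those receiving usual care".

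**The concern.** Poisson regression takes the variance of the outcome to equal its mean, p. For a yes/no outcome the variance is p(1−p), so the model-based Poisson variance is too large by a factor of 1/(1−p). That is trivial for a rare event and large for one expected in 59% to 79% of people. A sandwich variance removes the problem, but none is stated.

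The open choice matters in a second way. Logistic regression reports an odds ratio and Poisson a rate ratio, while the targets are stated as differences in rates. A result of 59% v 69% reads as an odds ratio of (0.69/0.31)/(0.59/0.41) = 1.55 or a rate ratio of 0.69/0.59 = 1.17. Both are correct descriptions of one result, but the plan lets the choice be made after the data are seen.

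At stake are the width of the intervals around the main comparisons and the chance of detecting a real gain between the two outreach arms.

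**Working it through.** **Inputs.** Usual-care rate 0.59, 10-point steps and 775 per arm (section 2.5). This gives 0.59, 0.69 and 0.79 if the percentages in section 1.1 are read as points. Independence is the plan's own approximation. Alpha is 0.05; sidedness is not stated, so two-sided is assumed.

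**1. The plan's own figure.** A two-proportion comparison with pooled variance at 775 per arm gives power of 98.4% for 0.59 v 0.69 and 99.5% for 0.69 v 0.79. At the 770 quoted in section 1.1 the figures are 98.4% and 99.4%. The statement of more than 80% therefore holds on its own inputs.

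**2. Standard errors of the log rate ratio, n per arm.**

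- Model-based Poisson: √[(1/p₁ + 1/p₂)/n]
- Correct (binomial): √[((1−p₁)/p₁ + (1−p₂)/p₂)/n]

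| Contrast | Poisson SE | Correct SE | Ratio |
|---|---|---|---|
| Usual care v medium (0.59 v 0.69) | √(3.144/775) = 0.0637 | √(1.144/775) = 0.0384 | 1.66 |
| Usual care v high (0.59 v 0.79) | 0.0618 | 0.0352 | 1.76 |
| Medium v high (0.69 v 0.79) | √(2.715/775) = 0.0592 | √(0.715/775) = 0.0304 | 1.95 |

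A fitted Poisson model with model-based and sandwich errors gives the same ratios, 1.658 and 1.949, for the first and third rows.

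**3. Power if Poisson errors are used.** Power = Φ[(ln(p₂/p₁) − 1.96 × SE_Poisson)/SE_correct].

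- Medium v high: (0.1353 − 1.96 × 0.0592)/0.0304 ≈ 0.64, power 73.8% (74.1% in 400,000 simulated trials). With the correct SE in both places it is 99.4%. Simulated logistic regression gives 99.5%.
- Usual care v medium: 79.6% (simulation 79.9%).
- Usual care (775) v both outreach arms pooled (1,550), with only a 10-point gain in each: 91.4%.

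Reaching 80% for medium v high with Poisson errors would take 849 per arm. The test is conservative: simulated type I error at 0.69 v 0.69 is about 0.0005 instead of 0.05.

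**4. Lower uptake.** Section 2.4 excludes people already up to date, while 59% is a current population rate, so uptake among those eligible could be lower. The documents give no figure; the range below is assumed, with 10-point steps and 775 per arm.

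| Usual care | Medium v high | SE too wide by | Power with Poisson SE |
|---|---|---|---|
| 10% | 0.20 v 0.30 | 15% | 98.7% |
| 30% | 0.40 v 0.50 | 34% | 90.3% |
| 40% | 0.50 v 0.60 | 48% | 84.7% |
| 48% | 0.58 v 0.68 | – | 80.1% |
| 49% | 0.59 v 0.69 | 66% | 79.6% |
| 59% | 0.69 v 0.79 | 95% | 73.8% |

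The fall below 80% needs usual-care uptake of about 49% or more.

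**5. Clustering.** Correlation within communities inflates the true variance by a design effect. For medium v high the Poisson variance is 2.715/0.715 = 3.80 times the independent binomial variance, so a design effect of 3.80 would make it right by accident. With six communities per arm (section 1.1), 775/6 ≈ 129 per community, and the matching intra-class correlation (ICC) is (3.80 − 1)/(129 − 1) ≈ 0.022. With 16 per intervention (also stated, in section 2.3), 775/16 ≈ 48, and it is 2.80/47 ≈ 0.06. A larger ICC would make Poisson intervals too narrow. Ordinary logistic intervals would be too narrow under any positive ICC; at a design effect of 3.80 the true SE is √3.80 = 1.95 times the reported one.

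**The case against.** The strongest reply is that the plan does not commit to the faulty analysis. Logistic regression is named first, has the right variance under independence and gives about 99.5% power. The plan is silent on variance; it does not choose the model-based form, and a careful analyst would probably add a sandwich estimator. This stands, and it is why the point is conditional.

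A reader might infer that the plan's intervals are wrong as written, or that its power statement is false. The documents support neither. No single model or variance is fixed, and the power statement is met on its own inputs. Nor do the figures of 66% to 95% predict the trial's actual intervals, because they assume independence in a trial randomised by community.

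Three further replies are fair. Usual care v any intervention, one of the two contrasts that sized the trial, keeps 91% power even with Poisson errors. Under independence the error is conservative and cannot produce false claims of benefit. Making the risk difference the sole primary scale would be largely a matter of preference.

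It might also be said that section 2.5 names the community as the analytic unit, which could imply a community-level analysis. No such method is described, and adjustment for age and sex suggests person-level models. Collapsing to community counts with a log-denominator offset would not help: the model-based Poisson error for the arm effect would be the same.

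**Conclusion.** The point holds as a conditional one and should be corrected. One analysis that section 2.5 permits would overstate standard errors by 66% to 95% and take medium v high power to about 74%, below the plan's own figure. This rests on model-based Poisson variance being used, independence, usual-care uptake of 59%, 10-point steps and 775 per arm. It does not arise with logistic regression or a sandwich variance, and below about 49% usual-care uptake the errors are still too wide but power stays above 80%. If the percentages are relative (0.59, 0.649, 0.708), medium v high power is already about 70% with correct variance and would be about 17% with Poisson errors.

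This is more than a missing detail. Neither model as written accounts for randomisation by community, so the permitted analyses can err in opposite directions, and the net error cannot be known in advance.

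**What to change.** In section 2.5, before outcome data are seen:

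- Name one primary model: a binomial or logistic model, or a Poisson model with sandwich variance.
- State that the variance is clustered on community, with a small-sample correction, since there may be as few as six communities per arm.
- State that model-based Poisson variance will not be used.
- Report the difference in percentage screened with a 95% confidence interval alongside the model's ratio, for high v medium and for the comparisons with usual care, because the targets are differences in rates.

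The cost is one or two sentences and standard software options; no new data are needed. The downside is that intervals may be wider than those from an analysis that ignores clustering.
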